## 4.2.2 Secondary Endpoint

For the second aims (a) and (b) looking at lung tissue inside the radiation field, the images will be processed similar to primary endpoint. For lung tissue inside the radiation field, changes in tracer uptake at the global lung, regional lung, and lung image voxel scales (compared to baseline scan) will be plotted against the radiation dose at the same scales to generate multiscale radiation dose response curves. These curves will be fit to linear and sigmoid dose-response functions. We will also separate out lung regions in the upper quartile and lower quartile of ventilation and perfusion, and generate separate radiation dose response curves per region, to assess for potential differences in radiation dose response of functional lung versus non-functional lung.

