## 1.0 INTRODUCTION

Title	Pulmonary Functional Imaging for Radiation Treatment Planning for Lung Cancer
Short Title	SPECT/CT for Radiation in Lung Cancer
Phase	Pilot Study
Methodology	Single Arm Open-Label
Study Duration	2 years
Study Center(s)	University of Washington Medical Center
Objectives	To utilize SPECT/CT imaging with 99mTc-MAA and 99mTc-DTPA to accurately identify functional lung in patients receiving radiation treatment for lung cancer, and characterize tissue response to radiation. The long-term goal being to use functional imaging to guide radiation treatment planning, so functional lung tissue can be preferentially avoided, which will reduce radiation induced pulmonary toxicity allowing for increased dose delivery to the primary tumor.
Number of Subjects	20 evaluable subjects
Diagnosis and Main Inclusion Criteria	Patients diagnosed with non-metastatic lung cancers receiving radiation treatment, with impaired pulmonary function
Study Product, Dose, Route, Regimen	99mTc-MAA and 99mTc-DTPA SPECT/CT scans
Duration of administration	Drug administration will consist of 3 SPECT/CT scans with 99mTc-MAA and 99mTc-DTPA (one baseline scan which is standard of care, two follow up scans which are experimental and paid for by departmental research funds). The two experimental scans will be at mid-radiation treatment and approximately 3 months post-treatment.
Statistical Methodology	Outside the radiation field, normal lung tissue ventilation and perfusion over serial imaging will be assessed for stability using regression analysis, Pearson correlation, and Dice coefficient. Inside the radiation field, dose response curves will be developed for radiation dose versus changes in ventilation and perfusion. Gradient search algorithm in MIM 6.0. will be used to identify perfused and ventilated lung.

This document is a protocol for a human research study. This study is to be conducted according to US and international regulations, applicable government regulations and Institutional research policies and procedures.

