## 3.0 STUDY OBJECTIVES

### 3.1 Primary Objective

To utilize SPECT/CT imaging with  $^{99m}\text{Tc}$ -MAA and  $^{99m}\text{Tc}$ -DTPA to identify functional lung on serial imaging in patients receiving radiation treatment for lung cancer, as well as to characterize reproducibility of perfusion and ventilation in non-irradiated lung tissue.

Hypothesis: For lung tissue outside the radiation field, perfusion and ventilation as defined by SPECT/CT imaging with  $^{99m}\text{Tc}$ -MAA and  $^{99m}\text{Tc}$ -DTPA will exhibit smaller changes over time than tissue inside the radiation field. Compared to the pre-radiation scan, lung tissue receiving radiation dose below the 20th percentile of total lung will have perfusion and ventilation that remain constant or increase at the mid-radiation treatment scan and 3-months post-treatment scans. By contrast, lung tissue receiving radiation dose above the 80th percentile of total lung will have perfusion and ventilation that decrease at the mid-radiation treatment scans and 3-months post-treatment scans.

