### 3.2 Secondary Objective

a) To estimate the dose response relationship on multiple spatial scales (global lung, regional lung, lung image voxel) between radiation dose and changes in lung ventilation and perfusion, both acutely (mid-radiation treatment) and long term (3 months post-treatment), using SPECT/CT imaging with  $^{99m}\text{Tc}$ -MAA and  $^{99m}\text{Tc}$ -DTPA.

Hypothesis: Compared to the current models of radiation dose response for lung tissue, using CT in addition to SPECT imaging acquired in the radiation treatment position, a more accurate regional dose response relationship between radiation dose and changes in lung function can be generated with superior volumetric and quantitative data.

b) To estimate the degree of radiation response in lung tissue with varying levels of function (i.e. compare radiation dose response of well ventilated and well perfused tissue against lung tissue with poor perfusion and ventilation). This may establish a threshold of lung tissue that would be “safe” to treat without significantly affecting lung function.

Hypothesis: Well-perfused and ventilated lung tissue has a different radiation dose response curve than lung tissue that receives poor ventilation and perfusion (upper quartile versus lower quartile of perfused and ventilated tissue image intensity distributions). The dose-response relationship can be modeled either as a linear or sigmoid function.

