### 4.2 Endpoints

#### 4.2.1 Primary Endpoint

In this study, patients with lung cancer will undergo SPECT/CT imaging with  $^{99m}\text{Tc}$ -MAA and  $^{99m}\text{Tc}$ -DTPA at the time of radiation treatment planning. All image datasets will be imported into MIM 6.0, and fused with the radiation treatment planning CT and radiation plan. Lung tissue will be divided into tissue outside the radiation field (dose < 20th percentile of total lung dose) and tissue inside the radiation field (dose > 80th percentile of total lung dose). This process will be repeated for the mid-treatment scan and 3 months post-treatment scan. Lung tissue outside the radiation field will be compared on serial scans and their perfusion and ventilation quantified. There should be insignificant changes in perfusion and ventilation in >80% of lung tissue outside the radiation field. Lung tissue inside the radiation field will also be compared, and should yield significant differences in ventilation and perfusion between pre, mid, and post-treatment scans.

We will analyze the perfusion and ventilation data through multiple methods. Image sets from all 3 time points (before radiation, mid-radiation, 3-months post-radiation) will be fused using rigid registration. Regions of interest within the lung will be defined using automated and semi-automated methods, including simple thresholds and gradient-search algorithms. For each tracer, uptake value will be calculated for each voxel. For lung tissue outside the radiation field, summary statistics such as total regional uptake and mean regional uptake by lobe will be compared across the time points using parametric and non-parametric statistical testing. Voxel-based correlation, including Pearson linear and Spearman rank, will be performed to measure the stability of uptake between time points. Lastly, metrics of ventilation and perfusion volume overlap between time points will be estimated using the Dice coefficient.

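### The secondary dose-response curves are tied to in-field lung, defined only as the top 20% by dose, which conflicts with the global-lung scale and with objective 3.2

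*Combined protocol and SAP*

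**What the plan says.** Section 4.2.1 splits the lung for the primary endpoint into tissue outside the field (dose below the 20th percentile of total lung dose) "and tissue inside the radiation field (dose > 80"th percentile). The hypothesis in section 3.1 uses the same two cuts. The documents contain no other definition of the field.

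Section 4.2.2 then applies the term to both secondary aims: "For the second aims (a) and (b) looking at lung tissue inside the radiation field, the images will be processed similar to primary endpoint". The next sentence repeats it ("For lung tissue inside the radiation field, changes in tracer uptake at the global lung, regional lung, and lung image voxel scales") and says that these changes "will be plotted against the radiation dose at the same scales to generate multiscale radiation dose response curves". Linear and sigmoid functions are fitted to the curves, and separate curves are drawn for the upper and lower quartiles of function. The synopsis (section 1.0, Statistical Methodology) carries the same restriction: "Inside the radiation field, dose response curves will be developed for radiation dose versus changes in ventilation and perfusion".

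The objectives are wider. Objective 3.2(a) is "To estimate the dose response relationship on multiple spatial scales (global lung, regional lung, lung image voxel"), with no mention of the field. The hypothesis for 3.2(b), "Well-perfused and ventilated lung tissue has a different radiation dose response curve than lung tissue that receives poor ventilation and perfusion", has no field limit either. Section 7.1 says that the baseline scan identifies functional lung on both sides of the field boundary and that the dose-response curves come from the scan data. It adds no restriction and does not redefine the term.

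**The concern.** One term is doing two jobs. As a stratum for the primary inside-versus-outside contrast, a cut at the 80th percentile is workable. As the population for a dose-response curve, it removes every dose at or below the patient's own 80th percentile, which is most of the range over which a curve has to be estimated. It also clashes with the global scale in the same sentence, because the top fifth of the lung by dose is not the whole lung.

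These curves are the product of both secondary aims. With a truncated dose range, the linear slope is less precise. A sigmoid is poorly located when its midpoint lies near or below the cut, because its low-dose plateau is then hardly observed. Section 3.1 predicts that lung below the 20th "percentile of total lung will have perfusion and ventilation that remain constant or increase at the mid-radiation treatment scan" and the later scan, so the plan itself expects the low-dose end to behave differently, yet that end would be off the curve. Two analysts could also fit different tissue and both claim to follow the protocol.

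**Working it through.** The plan states no figure on this point (no power calculation, dose distribution, midpoint or noise level), so there is nothing to reproduce. What follows from the definitions comes first, then an illustration under assumptions.

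**From the definitions** (taking the percentile over each patient's own lung voxels, the natural reading, though the protocol does not spell it out)
- In the fits: 1 − 0.80 = 20% of lung. Left out: 80%.
- In neither stratum: 0.80 − 0.20 = 60%.
- Per function-quartile curve: 25% × 20% = 5% of lung if function and dose are unrelated, against 25% if all lung is used.

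**Readings of the global scale**
- In-field change against in-field dose: the two axes match, but the point is not global.
- In-field change against whole-lung dose: the axes describe different tissue.
- Whole-lung change against whole-lung dose: this fits objective 3.2(a), but drops the restriction that opens the sentence.

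**Linear slope (assumed dose distributions).** Twelve were used: two uniform (0–60 and 0–45 Gy), three capped exponential (means 10, 15 and 20 Gy), three scaled beta and four low/high mixtures. Their 80th percentiles run from 16 to 48 Gy.
- At equal voxel number, the standard error ratio is SD(dose, all lung) / SD(dose, top 20%). With independent voxels, multiply by √5 because one fifth of them remain.
- Uniform, width w: (w/√12) / (0.2w/√12) = 5.0, and 5.0 × √5 = 11.2.
- Capped exponential, mean 15 Gy: 2.78 with independent voxels, so 2.78/√5 = 1.24 at equal number. One low/high mixture: 4.14, so 1.85.
- All twelve: 1.05–5.0 at equal number (median 1.9); 2.3–11.2 with independent voxels (median 4.3).
- Mean in-field dose is 26–54 Gy against a mean lung dose of 10–30 Gy, a ratio of 1.8 to 3.2.

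If true slopes vary between patients with SD τ, the ratio is √[(τ² + s²/((n/5)·SD²top)) / (τ² + s²/(n·SD²all))], with residual SD s = 25 points and n effective voxels per patient. For uniform 0–45 Gy, SD²all = 168.75 and SD²top = 6.75:
- τ = 0.3 points/Gy, n = 250: √[(0.09 + 625/337.5) / (0.09 + 625/42,187.5)] = √(1.942/0.1048) = 4.3. Over the twelve: 1.4–4.3, median 1.6.
- τ = 0.5, n = 1000: √[(0.25 + 0.463) / (0.25 + 0.0037)] = 1.7. Over the twelve: 1.04–1.7.

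**Sigmoid midpoint (simulation, all inputs assumed).** 150 runs; 20 patients with 250 effective voxels each; plateau −60 points; logistic scale 5 Gy; noise SD 25; per-patient session shift SD 5; patient 80th percentiles about 19–32 Gy. A pooled four-parameter logistic was fitted with bounds (midpoint 0–60 Gy, low-dose plateau −30 to 30 points, drop 0–130 points, scale 1–20 Gy). The 5–95% ranges of the estimated midpoint are:

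| True midpoint (Gy) | In-field only | All lung | Ratio of widths |
|---|---|---|---|
| 15 | 3.7–22.9 | 14.3–15.7 | 19.2/1.4 = 13.7 |
| 25 | 19.0–28.5 | 24.4–25.7 | 9.5/1.3 = 7.3 |
| 30 | 25.4–32.7 | 29.2–30.8 | 7.3/1.6 = 4.6 |
| 40 | 38.6–41.4 | 38.9–41.4 | 2.8/2.5 = 1.1 |
| 50 | 47.7–55.3 | 47.6–54.3 | 7.6/6.7 = 1.1 |

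A second simulation with separate code gave the same pattern, for example 7.0–22.7 against 14.4–15.7 at 15 Gy. With a low-dose gain of 5 or 10 points, as section 3.1 allows, the ratios are 16–17 at 15 Gy, 5.9–7.1 at 25 Gy, 3.9–4.0 at 30 Gy and about 1.2 at 40–50 Gy.

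**Truncation or fewer voxels?** Against a random 20% of all voxels (120 runs, gain 0 or 10 points), the in-field range is 8.8–10.4 times wider at 15 Gy and 2.9–3.5 times wider at 25 Gy, but only 0.5–0.7 times as wide at 40–50 Gy. The loss at low midpoints therefore comes mainly from truncation. At high midpoints in-field voxels are the more informative ones, and the small net loss comes from having fewer of them.

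**The case against.** The percentile rule was written for the primary contrast. The phrase about processing the images as for the primary endpoint need not import the cut. Global, regional and voxel can be read as levels of aggregation, with global meaning one pooled in-field value per patient. Section 7.1 and objective 3.2 carry no restriction, so the authors may have meant any irradiated lung. On that view this is a reused term, not a contradiction. The size is also driven by assumptions: the largest slope ratios come from uniform dose distributions, the 15 Gy case places the midpoint below the simulated cut by construction, and at 40–50 Gy little is lost. Low-dose lung is still examined under the primary endpoint, voxel data exist for the whole lung, and full-range curves could be fitted later.

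Much of this stands as a limit on the size. The harm may be small or large depending on a midpoint nobody has stated, and the intended meaning may have been wider. It does not remove the point. No text gives the wider meaning, and the restriction appears twice in 4.2.2 and again in the synopsis, so it is not a single slip. The pooled reading of global still leaves low and middle doses off the curve. Section 7.1 adds to the mismatch without resolving it. The primary endpoint's low-dose summary is not placed on the curve, and the middle 60% is in neither stratum.

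**Conclusion.** The concern holds. As written, section 4.2.2 and the synopsis limit the secondary curves to lung above the 80th percentile of dose, at odds with the global scale in the same sentence and with objective 3.2. The 20%, 80%, 60% and 5% shares follow from the definition if percentiles are taken within each patient's lung (and, for the 5%, if function and dose are unrelated). The loss of precision is illustrative only: modest to large for a linear slope, severe for a sigmoid midpoint near or below the cut, and slight for one well above it. The primary endpoint is not touched and no data are lost. This should be fixed before analysis, but it is a correction to a secondary estimation aim in a 20-subject pilot, not a threat to the study. Confidence is medium, because the authors may have intended a wider meaning.

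**What to change.** Reconcile the synopsis and sections 3.2, 4.2.1, 4.2.2 and 7.1 so that the tissue entering each curve is stated once.

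- In 4.2.2, including its opening phrase on aims (a) and (b), and in the synopsis, specify that the linear and sigmoid curves, overall and by function quartile, are fitted to all normal lung over the full dose range. State what the global and regional points are and which dose each is plotted against.
- Keep the 20th/80th percentile split for the primary inside-versus-outside comparison.
- Report any in-field-only curve as an additional analysis.
- If any irradiated lung was meant, give that tissue its own definition in 4.2.2, separate from the 80th-percentile rule.

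The cost is two or three sentences. No new data are needed: section 4.2.1 already calculates uptake for each voxel and fuses the scans with the radiation plan.

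### Voxel- and region-scale dose-response fits, the quartile contrast and the lobar tests have no patient-level term, although the independent unit is the patient (n = 20)

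*Combined protocol and SAP*

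**What the plan says.** Section 1.0 sets the size at "20 evaluable subjects" and gives no calculation behind it.

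Section 4.2.1 works at voxel level ("For each tracer, uptake value will be calculated for each voxel"). It then does three things outside the field:
- total regional uptake and mean uptake by lobe are tested across time points, by parametric and non-parametric tests that are not named;
- "Voxel-based correlation, including Pearson linear and Spearman rank, will be performed to measure the stability of uptake between time points";
- volume overlap between time points is measured by the Dice coefficient.

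Section 4.2.2 takes tissue inside the field. Change from baseline, at the global lung, regional lung and voxel scales, "will be plotted against the radiation dose at the same scales to generate multiscale radiation dose response curves". On the model, the section says only this: "These curves will be fit to linear and sigmoid dose-response functions". For aim (b), lung is split by upper and lower quartile of function, to "generate separate radiation dose response curves per region, to assess for potential differences in radiation dose response".

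Neither section mentions a fit per patient, a patient random effect, a clustered variance, a bootstrap over patients or spatial correlation between voxels. No separate statistics section supplies one.

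**The concern.** Voxels within one patient share that patient's lungs, treatment plan, chemotherapy, breathing pattern and registration error. Their responses to dose are therefore not independent, and adding voxels does not add patients. A linear or sigmoid least-squares fit to voxels stacked over patients, or a standard test on lobes stacked over patients, counts each row as a new observation.

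This matters because the plan wants conclusions and not only pictures. Section 3.2 hypothesises that well and poorly functioning lung have different dose-response curves, and hopes to find a threshold of lung that could be irradiated safely. Section 4.2.1 expects significant differences inside the field and plans statistical testing outside it. If those conclusions rest on row counts, a difference that reflects variation among 20 patients could be read as a firm property of lung tissue and carried into later radiation planning work.

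**Working it through.** The plan gives no standard error, alpha, power or p-value, so there is no figure to reproduce. The check asks how large the error is if rows are pooled.

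**Inputs.** Patients K = 20 (section 1.0). Everything else is assumed: two-sided alpha 0.05, m voxels per patient, within-patient dose variance v, voxel residual variance σ², and between-patient SD τ of the dose slope. The true mean slope is zero and voxels are independent given the patient.

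**Voxel-scale slope.** Pooled regression reports a slope variance of about σ²/(K·m·v). The true variance is about τ²/K + σ²/(K·m·v). Hence:
- SE ratio (true/reported) R = √(1 + m·v·τ²/σ²)
- true type I error ≈ 2[1 − Φ(1.96/R)]

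*Setting A:* m = 2,000, σ = 20, dose uniform over 0 to 60 Gy, so v = 60²/12 = 300.

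| τ per Gy | m·v·τ²/σ² | R | Formula | Simulated, pooled |
|---|---|---|---|---|
| 0.05 | 3.75 | 2.18 | 37% | 35–37% |
| 0.1 | 15 | 4.00 | 62% | 57–60% |
| 0.3 | 135 | 11.7 | 87% | 87% |

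A t-test on the 20 patient slopes rejected in about 4% to 6% of the same simulated studies. With dose restricted to 20 to 60 Gy, pooled rejection was 21%, 42% and 74%, against 3% to 4% at patient level.

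*Setting B:* dose uniform on 0 to 1 (v = 1/12), voxel noise SD 1 and patient intercept SD 0.3. In the pooled fit σ² = 1 + 0.09 = 1.09.

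| m | τ | R | Formula | Simulated, pooled | Patient-level |
|---|---|---|---|---|---|
| 1,000 | 0.05 | √1.19 = 1.09 | 7% | 5.9% | 3.8% |
| 1,000 | 0.2 | √4.06 = 2.01 | 33% | 33.1% | 5.3% |
| 5,000 | 0.05 | √1.96 = 1.40 | 16% | 16.3% | 5.6% |
| 5,000 | 0.2 | √16.3 = 4.04 | 63% | 62.2% | 4.3% |

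With 1,000 runs, the Monte Carlo standard error of the 5.9% is √(0.059 × 0.941/1,000), about 0.7 points.

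**Quartile contrast.** With 500 voxels per quartile, the Setting A residual and slope SDs, and patient slopes drawn independently in the two quartiles, the pooled comparison rejected in 15%, 36% and 70% of studies. A paired patient-level test rejected in 4% to 6%. If a patient's two slopes move together, part of τ cancels and the inflation is smaller.

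**Lobar tests.** For a mean change pooled over five lobes per patient, the design effect is 1 + (5 − 1)·ICC.
- ICC 0.1: 1.4; SE ratio √1.4 = 1.18; type I error 2[1 − Φ(1.96/1.18)] ≈ 10%.
- ICC 0.5: 3.0; SE ratio √3.0 = 1.73; type I error ≈ 26%.

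Spatial correlation between neighbouring voxels is in none of these figures. It would increase the voxel-scale ones.

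**The case against.** The strongest reply is that the plan is silent here, and that silence is not a wrong analysis. Much of that stands.

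- Pooling across patients is not stated. Registration is of one patient's serial scans, so a voxel correlation or a Dice coefficient between time points is naturally a within-patient quantity. As a descriptive measure of agreement it needs no independence between voxels.
- The global-lung scale has one value per patient, tracer and time point, so the patient is already the unit there.
- No standard error, interval or p-value is named for the correlations or curves. The secondary aims are worded as estimation, in a single-arm pilot.
- If lobes are tested one at a time, each test has at most 20 patients and the lobar inflation above does not arise.

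A reader might infer that the whole plan treats voxels as the unit, so that all its standard errors must be far too small. The documents do not support that, for the reasons just given. A reader might also apply a design effect to the voxel count. Assuming a 3.5 L lung and 4.4 mm voxels, a 20% region holds about 8,200 voxels. ICC 0.01 to 0.10 then gives design effects of 83 to 823 and standard errors 9 to 29 times too small. That formula describes a pooled mean change, not a dose slope, and every input to it is assumed.

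What the reply does not remove is that curves at voxel and region scale must be combined over patients somehow, that the only methods listed carry no patient term, and that sections 3.2 and 4.2.1 call for comparative conclusions.

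**Conclusion.** The concern holds in a conditional form. For the voxel- and region-scale dose-response fits, the quartile contrast and any test that stacks lobes, the plan names no method that respects the patient as the independent unit. Applied to pooled rows, the listed methods give standard errors that are too small.

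How much too small cannot be known from the documents. Pooled-slope type I error runs from barely above nominal (about 6%) to 87%, driven mainly by the voxel count and by how much dose slopes differ between patients. A test on patient slopes stays near 5% throughout. Five pooled lobes give about 10% to 26% for ICC 0.1 to 0.5; patients with earlier lobectomy or pneumonectomy, who are eligible, contribute fewer lobes. All of this assumes a two-sided 5% level. The global-lung curves and within-patient correlation and Dice values are not at fault in themselves. This should be settled before analysis, because the valid method is simple and the invalid one is easy to run by default.

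**What to change.** In section 4.2.2:
- State that the patient is the unit of inference.
- Fit each voxel- and region-scale curve within patient and summarise the 20 patient-level parameters, or use a mixed model with patient random intercept and slope. The mixed model helps where one patient's dose range is too narrow to identify a sigmoid.
- Take confidence intervals from a bootstrap that resamples whole patients, which also carries the spatial correlation within each patient.
- Test the upper- versus lower-quartile contrast as a paired within-patient difference.
- Leave the global-lung curve as one point per patient, tracer and time point.

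In section 4.2.1:
- Compute voxel correlations and Dice per patient and report their distribution over patients.
- Test lobar changes with the patient as the cluster, or state that each lobe is tested separately over patients.

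The cost is a paragraph of analysis wording and a little programming. No scans or patients are added. Intervals become wider, which reflects what 20 patients can support.

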## **7.1 Imaging Protocol**

SPECT/CT with 99mTc-MAA and 99mTc-DTPA will be performed per standard protocol, which is currently in routine clinical use. The imaging session is comprised of an inhalation of the 99mTc-DTPA tracer and SPECT static acquisition, followed by intravenous injection of the 99mTc-MAA tracer and second SPECT static acquisition. This rapid serial process ensures the efficient imaging of ventilation and perfusion in the same imaging session. An initial scan at the time of radiation planning will identify functional lung that is ventilated and perfused. This scan will be in the radiation treatment position which can be fused precisely with the radiation treatment planning scan, and will be used to identify functional lung tissue both inside and outside the radiation fields. Two follow up scans will track lung response to radiation (one scan at mid-treatment for acute radiation response, and one scan at 3-months post-treatment for longer term assessment). Detailed ventilation and perfusion dose response curves will be generated from this data. Comparison planning with proton radiation will be performed to evaluate the feasibility of improved functional lung sparing with proton beam radiation.

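### Setting uptake quartiles on the same scan that anchors the change would make the two dose-response curves of aim 3.2(b) differ in level through regression to the mean, at voxel scale or in threshold-built regions

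*Combined protocol and SAP*

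**What the plan says.** Objective 3.2(b) asks whether well-functioning and poorly functioning lung respond differently to dose, taking "upper quartile versus lower quartile of perfused and ventilated tissue image intensity distributions". On the use of the answer it says "This may establish a threshold of lung tissue that would be" safe to treat.

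Section 4.2.2 carries this out in in-field lung. The outcome is "changes in tracer uptake at the global lung, regional lung, and lung image voxel scales (compared to baseline scan"), plotted against dose and fitted with linear and sigmoid functions. For aim (b) the plan will "separate out lung regions in the upper quartile and lower quartile of ventilation and perfusion, and generate separate radiation dose response curves per region".

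Neither section names the scan that sets the quartiles, and neither says whether change is percent or absolute. Section 4.2.2 speaks of regions and section 3.2 of intensity distributions, so the unit sorted is not settled either. Two other places bear on this:

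- Section 7.1 says of the initial planning scan that it "will be used to identify functional lung tissue both inside and outside the radiation fields".
- Section 4.2.2 says "the images will be processed similar to primary endpoint". Under that endpoint, section 4.2.1 states: "Regions of interest within the lung will be defined using automated and semi-automated methods, including simple thresholds and gradient-search algorithms".

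Out-of-field lung is analysed for the primary endpoint by total uptake, lobe means, voxel correlation and Dice overlap. It is not split by baseline quartile or used as a reference for the secondary curves.

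**The concern.** If the initial scan sets the quartiles, one noisy image does two jobs: it sorts the tissue and it is the starting point of the change. Tissue that falls in the top quartile partly through noise tends to read lower next time, and tissue in the bottom quartile tends to read higher. This happens at every dose and needs no radiation effect. Because the curves use in-field lung only, no unirradiated tissue of the same baseline quartile shows how much of a gap is artefact.

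At stake is the reading of aim 3.2(b). On level, poorly functioning lung would look less affected than it is, which bears directly on the idea of a threshold of tissue that is safe to treat.

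**Working it through.** The plan gives no figure to reproduce: no between-scan correlation r, no coefficient of variation (CV) of uptake and no dose-response slope. These are therefore assumptions: r from 0.70 to 0.95, CV 40% (25% as an alternative), and a true effect of -1% per Gy in every voxel. The doses 21 and 41 Gy are illustrative.

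**Step 1: no radiation effect.** For a normal distribution the mean of the top quartile is pdf(0.674)/0.25 = 1.2711 SD above the overall mean, and the bottom quartile lies as far below. On a second scan with correlation r, each moves back by 1.2711 × (1 − r) SD. The gap is therefore 2 × 1.2711 × (1 − r) = 2.542 × (1 − r) SD. At r = 0.80 this is 2.542 × 0.20 = 0.51 SD.

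**Step 2: percent change with an identical true effect.** The follow-up/baseline ratio of summed uptake in a quartile is multiplied by

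(1 ± 1.2711 × r × CV) / (1 ± 1.2711 × CV), with plus for the upper quartile and minus for the lower.

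At r = 0.80 and CV 0.40:

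- upper: 1.4068/1.5084 = 0.9326
- lower: 0.5932/0.4916 = 1.2068

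At 21 Gy the true ratio is 0.79, so the readings are 0.9326 × 0.79 = 0.737 and 1.2068 × 0.79 = 0.953, or −26.3% and −4.7%. Fitted slopes are minus the same factors.

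| Assumed r | Gap, no effect (SD) | 21 Gy, truth −21%: upper v lower | 41 Gy, truth −41%: upper v lower | Slope, truth −1.00 %/Gy: upper v lower |
|---|---|---|---|---|
| 0.95 | 0.13 | −22.3% v −16.9% | −42.0% v −37.9% | −0.98 v −1.05 |
| 0.90 | 0.25 | −23.7% v −12.8% | −43.0% v −34.9% | −0.97 v −1.10 |
| 0.80 | 0.51 | −26.3% v −4.7% | −45.0% v −28.8% | −0.93 v −1.21 |
| 0.70 | 0.76 | −29.0% v +3.5% | −47.0% v −22.7% | −0.90 v −1.31 |

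With CV 25% the 21 Gy gap runs from 2.8 points (r = 0.95) to 16.8 points (r = 0.70). A simulation with independent noise on each scan agreed with the closed form within 0.3 points.

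**Step 3: absolute change.** With an additive effect, r = 0.80 and CV 40%, the offset is 1.2711 × 0.20 × 0.40 = 0.10 of mean uptake, down in the upper quartile and up in the lower, at every dose. Slopes stay equal.

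**Step 4: unit sorted.** A region made by thresholding the initial scan keeps the full voxel-scale shift, 0.51 SD at r = 0.80. For predefined regions of 10 voxels with a common true value and independent noise (the best case), Spearman-Brown gives r = 10 × 0.80/(1 + 9 × 0.80) = 0.976 and a gap of 0.06 SD.

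**Step 5: which scan.** In simulation at r = 0.80 with no effect, sorting on a follow-up scan reverses the gap (0.51 SD the other way). Sorting on the mean of the two scans gives about zero.

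**Step 6: does an out-of-field reference help?** With the same r in and out of field, the Step 2 factor cancels on division, and simulation returned about −21% and −41% in both quartiles. With r = 0.80 in field and 0.90 out of field, at 21 Gy:

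- upper: 0.9326/0.9663 × 0.79 = 0.762, or −23.8%
- lower: 1.2068/1.1034 × 0.79 = 0.864, or −13.6%

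The correction is then only partial.

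**The case against.** **The plan is not blind to the artefact.** A reader might infer that nothing planned could reveal it. That goes too far. In the Step 2 model the linear fit already planned has a 0 Gy intercept equal to the factor minus 1. Simulation at r = 0.80 gave −6.8% (upper) and +20.6% (lower), with slope/(1 + intercept) equal to −1.00 %/Gy in both quartiles. The planned voxel correlations would also supply r. This stands, with two limits: the intercept extrapolates a linear effect below the in-field doses, and the plan does not prescribe reading it this way.

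**Regional curves need not be affected.** The regional case depends on thresholds being what builds the quartile regions. Section 4.2.1 lists thresholds as one method among several and does not tie them to quartiles. This stands for predefined regions; the voxel-scale curves remain exposed.

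**The direction is not single.** A reader might infer that poorly functioning lung will always look more resistant. That holds for level. On percent-change slopes the lower quartile looks steeper, and on absolute change with an additive effect the slopes are equal. Objective 3.2(b) does not say whether level or slope is compared.

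**The sizes are all assumed, including the noise form.** With multiplicative noise at r = 0.80 (log-SD 0.385), the 21 Gy reading is −26.7% v −10.9% instead of −26.3% v −4.7%. The figures here are ratios of summed uptake and do not describe averages of voxel-by-voxel percent changes.

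**The correction can mislead.** Section 3.1 allows out-of-field uptake to rise. If it rose 15% in the upper quartile and 5% in the lower (assumed), an identical −21% would read 0.79/1.15 = 0.687 (−31%) v 0.79/1.05 = 0.752 (−25%). The uncorrected curves lean the same way. A mid-to-3-month check would show 0% v 0% if the rise were complete by the mid scan, which section 7.0 allows up to 1 week after radiation ends. A rule that accepts any difference seen in both versions would therefore pass a pure artefact. This stands, and is why the reference should be a sensitivity analysis.

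**Conclusion.** The concern holds in a limited form. On the natural reading of sections 4.2.2 and 7.1, the between-quartile contrast of aim 3.2(b) is biased in level at voxel scale or for threshold-built regions, and in slope too if change is percent. With no radiation effect the gap is 0.13 to 0.76 SD for r from 0.95 to 0.70, and it is zero at r = 1. The size rests wholly on assumed r, CV and noise form. That the initial scan sets the quartiles is itself an inference. Since the choice of scan can reverse or remove the gap, leaving it unnamed matters.

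The bias does not reach the global-lung curves, the primary endpoint or any patient's treatment. The aim is a descriptive secondary one in a 20-subject pilot, and no test or decision is attached to it. The change is worth making because it is cheap and the contrast is exactly what the aim asks about.

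**What to change.** In section 4.2.2:

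1. State that quartiles are set on the initial scan, the unit sorted (voxel or predefined region), the cut-points, and whether change is percent or absolute.
2. Beside the uncorrected quartile curves, report as a sensitivity analysis the in-field change referenced to out-of-field tissue (dose below the 20th percentile) of the same baseline quartile. Divide follow-up/baseline ratios of summed uptake, or subtract the mean change if change is absolute. Report each curve's fitted 0 Gy intercept, which shows the artefact if the effect is linear.
3. Show out-of-field change by baseline quartile, from baseline and from the mid scan to 3 months. Neither later scan set the quartiles, so with independent scan noise a quartile difference between them is real drift.
4. Adopt no fixed interpretation rule. State that a level difference between quartiles in the uncorrected curves alone is not evidence of a different radiation response. State too that the correction assumes similar reliability in and out of field, similar baseline uptake distributions, and no out-of-field change that differs by quartile.

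The cost is wording and a little more analysis. No new scans are needed, because section 4.2.1 already says: "Lung tissue outside the radiation field will be compared on serial scans and their perfusion and ventilation quantified". Intervals for the referenced contrast widen by sqrt(2 × (1 − correlation)) when the in-field and out-of-field contrasts have equal variance: about 1.4 times if they are independent, and not at all if they correlate at 0.5.
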